4.2 Double Blind Placebo Controlled Food Challenge (DBPCFC)

Protocol DBPCFCs will be administered on the subject at entry, 48 months and weekly during the seventeen-week tolerance phase by a nurse or physician who is blinded to the testing material. The supervising investigator will also be blinded to testing material. Before each challenge, the subject will have a physical exam and peak expiratory flow measurements performed.

The DBPCFC consists of two parts that will be randomly ordered. One part will consist of graded doses of peanut flour and the other of identical graded doses of placebo in the form of oat flour. The doses will be given every 10-20 minutes up to a cumulative dose of 1000 mg (25 mg, 50 mg, 100 mg, 250 mg, 575 mg) during the entry challenge and up to a cumulative dose of 5000 mg (100 mg, 200 mg, 500 mg, 800 mg, 1300 mg, 2100 mg) during the 48th month and final DBPCFC. There will be a minimum 10 minute observation period between doses to monitor for symptoms.

After administration of the first part of the challenge the subject will be observed for a minimum period of 1 hour prior to starting the second part. Reactions will be scored using a Food Challenge Symptom Score (FCSS) sheet. If the subject begins to have significant objective or persistent subjective symptoms, the food challenge will be terminated and the subject will be given appropriate treatment. Subjects who are symptomatic and receive treatment are observed for a minimum of 2 hours after the challenges are completed before being discharged from the clinical research unit.

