4.3 Method of Week Assignment for the Final Challenge and Randomization

The following criteria must be satisfied in order for the patient to continue to the SU phase of the study and be randomized:

1. The patient achieves MCRT at the 48th month DBPCFC to continue to the SU phase. This requires patient to be asymptomatic upon administration of 300 mg dose as assessed by Food Challenge Symptom Score sheet.
2. If subjects are found symptomatic and AEs that occur are considered to be intolerable at or below the MCRT, subjects will be refrained from taking the final challenge and will be considered to have lost their desensitization at week 0.
3. No subject will be administered a final challenge dose higher than the NOAEL attained at the 48th month DBPCFC.

Before the start of the SU phase of the study, a computer-generated block randomization schedule is prepared such that each subject has an equal probability of being randomized to one of the weekly challenges held in initial 6 weeks, between 7-12 weeks and between 13-17 weeks. Based on the randomization schedule, three qualified subjects are randomly assigned to one of the final DBPCFC administered each week during the study's 17-week SU phase.

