8.1.1 Statistical Assumptions

Time to Loss of Desensitization (TLD) requires more rigorous mathematical framework of stochastic process. However, a good approximation could be achieved using Interval Censoring framework for the latter three events defined in section 3.2.1 (bullet 3). The framework uses following assumptions:

- Desensitization is monotonically decreasing with time. $NOAEL(\text{final DBPCFC}) \leq NOAEL(48\text{th month DBPCFC})$
- Subject's true sensitivity threshold at the 48th month DBPCFC is approximated by his/her NOAEL.
- Subjects with the final DBPCFC NOAEL higher than the 48th month DBPCFC NOAEL will be regarded as exceptions. Their final DBPCFC NOAEL will be considered equal to the 48th month DBPCFC NOAEL for conservative time to loss of desensitization estimates.
- Subjects with 48th month LOAEL < MCRT will also fail at LOAEL administered at the final DBPCFC that are less than MCRT, thereby un-necessitating the need for the final DBPCFC.
- Since the final DBPCFC observation times are randomized, subject's unobserved time to loss of desensitization and the baseline covariates are independent of his/her final DBPCFC observation time.

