8.1.2 Event Censoring

- For efficacy endpoint in section 3.2.1 bullet 1 (population sensitization threshold), an individual's true threshold is
 - left censored if individual fails on the smallest dose administered
 - right censored if no adverse effect is observed on the largest dose administered
 - interval censored in all other cases.
- For the latter three time to loss of desensitization efficacy endpoints defined in section 3.2.1 bullet 2, censoring is defined as below:
 - Subjects with 48th month LOAEL < MCRT who are not administered the final DBPCFC have their time to loss of desensitization assumed to be zero.
 - Subjects with the final DBPCFC NOAEL equal to the highest administered dose level are assumed to have their LOAEL beyond the observed time.
 - For subjects who do not show up for the final DBPCFC until the 17th week of randomization will be removed from the analysis. A separate analysis will be conducted to predict drop-outs.

No censoring will occur on safety endpoints.

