10. EFFICACY ANALYSES

10.1 Primary Efficacy Analysis Approach

To begin with, our primary analysis will comprise of two parts.

First, an Interval-Censoring Survival Analysis (ICSA) approach will be used to analyze the 48th month DBPCFC threshold data (Collett, 1993, Chapter 9, Taylor et al - 2009). The methodology is appropriate when the exact dose that provokes a reaction in an individual is not known but it is known to fall into a particular interval. Using ICSA, if an individual had an objective reaction at the first dose in a challenge trial, then left-censoring occurred, and the NOAEL was set to zero with the LOAEL set as that first dose. If an individual did not experience an objective reaction after the largest challenge dose, then right-censoring occurred, and the NOAEL was set to that largest challenge dose (if a subjective response occurred at that largest dose, this was also considered as the objective NOAEL), while the LOAEL was set to infinity. In all other cases, interval-censoring occurs bounded by the NOAEL and LOAEL. Parametric (Log-normal, Weibull) and non-parametric dose-distribution model will be used to estimate the ED10 and the ED05, the doses predicted to provoke reactions in 10% and 5%, respectively, of the peanut-allergic population.

Second, for each dose interval bounded by the NOAEL and LOAEL of the 48th month DBPCFC, we will conduct survival analysis with case-1 censoring (Huang – Wellner lecture notes, Kosorok et al, 1998) to estimate time to loss of desensitization. We will assume exponential

distribution with log link for the decay of sensitivity threshold for those who take the final challenge. This assumption of exponential decay will be validated using semi/non-parametric analysis with an option for modeling with a more flexible **semi-parametric** distribution. The analyses will be performed with and without the effect of baseline and other clinical covariates. This analysis will provide an initial insight into effectiveness of peanut SLIT in longevity of induced clinical desensitization and SU.

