To illustrate, we introduce the following notation. Let X_d be the time to loss of desensitization with distribution F_d for a given NOAEL, d , administered at the 48th month DBPCFC ($d = 100, 200, 500, 800, 1300, 2100$ mg). Let T be an observation time (in weeks), $t = 0, 1 \dots 17$ with distribution G . Because the assignment time is randomized, the time of interest X_d and baseline covariates will be independent of T . We also assume that the clinically induced desensitization is monotonically decreasing such that the subject's NOAEL is either decreased or stays constant by observation time T . In other words, the true time to loss of desensitization from the 48th month DBPCFC, which is unknown, is either less or equal to the observation time. This could mathematically be represented as a problem of case-1 interval censoring wherein, we observe n i.i.d observations of $(T, I\{X_d \leq T\} | d) = (T, \Delta_d)$ for a given NOAEL, d . Further, we assume $X_d = 0$ for those subjects who do not meet MCRT ($d < MCRT$) at the 48th month DBPCFC. Let π define the probability that $X_d = 0$, and let the baseline and clinical covariates be represented by Z . Then, in order to derive the likelihood of F_d , we need to solve the following optimization problem to find the MLE:

$$\sup_{F \in \mathcal{F}} L_n(F)$$

, where \mathcal{F} is a class of distribution functions and

$$L_n(F) = \prod_{i=1..n} P(\beta, \gamma, Z_i, t)$$

$$\begin{aligned} P(\beta, \gamma, Z_i, t) &= \{P(X_{id} = 0) I(X_{id} = 0)\} * \{P(X_{id} > 0) I(X_{id} > 0)\} \\ &* \{P(X_{id} = t, \Delta = 0 | d, X_{id} > 0)\} * \{P(X_{id} = t, \Delta = 1 | d, X_{id} > 0)\} \\ &= \left[\frac{e^{\gamma' Z_i}}{1 + e^{\gamma' Z_i}} \right]^{y_i} * \left[\frac{1}{1 + e^{\gamma' Z_i}} \right]^{1-y_i} * [(1 - F_d(t))g(t)]^{1-\delta_i} * [F_d(t)g(t)]^{\delta_i} \\ &= \left[\frac{e^{\gamma' Z_i}}{1 + e^{\gamma' Z_i}} \right]^{y_i} * \left[\frac{1}{1 + e^{\gamma' Z_i}} \right]^{1-y_i} * (1 - F_d(t))^{1-\delta_i} * F_d(t)^{\delta_i} g(t) \end{aligned}$$

$$y_i = I(X_{id} = 0); \delta_i = I(\Delta_i = 1); F_d(t) = 1 - e^{-\lambda_i t}; \lambda_i(t, Z_i) = \lambda_0 e^{\beta' Z_i}$$

Maximizing the above likelihood will provide estimates of β & γ towards estimating distribution of time to loss of desensitization.

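### On the single-step doses that SAP 10.1 lists, its time-zero rule codes children who tolerate 300 mg in total and react at the 500 mg step as lost at week 0, contrary to SAP 4.3 and 8.1.2

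*SAP*

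**What the plan says.** SAP 4.2 describes the 48-month and final challenges as running "up to a cumulative dose of 5000 mg (100 mg, 200 mg, 500 mg, 800 mg, 1300 mg, 2100 mg"). SAP 4 gives the MCRT as 300 mg of peanut protein.

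The SAP says in several places who counts as lost at time zero:

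- **SAP 10.1**, notation for the primary likelihood: d is the 48-month NOAEL, with values "100, 200, 500, 800, 1300, 2100" mg. X_d is set to 0 "for those subjects who do not meet MCRT", with d < MCRT in parentheses.
- **SAP 8.1.2**: the time is zero for "Subjects with 48th month LOAEL < MCRT who are not administered the final DBPCFC".
- **SAP 8.1.1** uses the same LOAEL criterion as an assumption: "Subjects with 48th month LOAEL < MCRT will also fail at LOAEL administered at the final DBPCFC".
- **SAP 4.3 item 2** gives week-0 loss and no final challenge: "If subjects are found symptomatic and AEs that occur are considered to be intolerable at or below the MCRT".

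Entry to the withdrawal phase is in SAP 4.3 item 1, which asks that the child reach the MCRT: "This requires patient to be asymptomatic upon administration of 300 mg dose as assessed by Food Challenge Symptom Score sheet".

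The protocol is not consistent about a child who tolerates exactly 300 mg. The first synopsis bullet ends the study for children who cannot take more than 300 mg. The second randomises those who can take 300 mg or more. The Study Design section stops children below 300 mg and randomises those above it, so it gives no disposition for exactly 300 mg.

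**The concern.** SAP 10.1 compares a single-step amount with a threshold that the challenge reaches only by adding two steps. Children who clear the 300 mg bar and react at the next step are then treated as if they had not cleared it.

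The rule defines y_i, the time-zero indicator in the primary likelihood. A child with y_i = 1 contributes to the logistic part (π and γ) and not to the part for X_d > 0, where the randomised week and the final-challenge result enter. If such a child has been randomised and challenged, the literal rule replaces an observed result with a loss at week 0. The report would then describe a child who passed the SAP's own entry test as never desensitized. Two programmers working from different sentences of the same SAP would produce different primary datasets.

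**Working it through.** **Inputs.** Challenge steps from SAP 4.2 (the same in Protocol 5.6), levels of d and the time-zero rule from SAP 10.1, the second time-zero rule from SAP 8.1.2, the entry and week-0 rules from SAP 4.3, and MCRT = 300 mg from SAP 4.

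**1. What the listed doses are.** 100 + 200 + 500 + 800 + 1300 + 2100 = 5000 mg, which reproduces the stated cumulative total. The values of d are therefore increments. The running totals are 100, 300, 800, 1600, 2900 and 5000 mg. No single step is 300 mg; it is the total after step 2.

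**2. The two rules on the step scale.**

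| Reacts at | NOAEL | LOAEL | 10.1: NOAEL < 300 | 8.1.2: LOAEL < 300 |
|---|---|---|---|---|
| Step 1 | 0 | 100 | zero | zero |
| Step 2 | 100 | 200 | zero | zero |
| **Step 3** | **200** | **500** | **zero** | **not zero** |
| Step 4 | 500 | 800 | not zero | not zero |
| Step 5 | 800 | 1300 | not zero | not zero |
| Step 6 | 1300 | 2100 | not zero | not zero |
| None | 2100 | infinity | not zero | not zero |

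The rules differ only for step-3 reactors. Changing < to ≤ alters neither entry in that row, because 200 is below 300 and 500 is above it.

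**3. Disposition of a step-3 reactor.** The child has taken 100 + 200 = 300 mg without symptoms. SAP 4.3 item 1 admits the child to the withdrawal phase, item 2 does not apply, and the second synopsis bullet randomises the child. On this reading 8.1.2 is right at all seven levels and 10.1 is wrong at one.

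**4. Moving to cumulative doses only.** A step-3 reactor now has NOAEL 300 and LOAEL 800. With < as written, neither rule gives zero, so they agree on this child. A step-2 reactor, however, has NOAEL 100 and LOAEL 300. SAP 10.1 gives zero, but 8.1.2 does not, because 300 is not below 300. Under the SAP 4.3 entry rule, 10.1 is therefore right only on the cumulative scale and 8.1.2 only on the step scale. Item 2 of SAP 4.3 is right on both: steps 1 and 2 are at or below 300 mg (100 and 200, or 100 and 300), and step 3 is above it (500, or 800).

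**5. Size.** Let p be the true proportion of this stratum that loses desensitization by week 17, and s its share of challenged children. Coding the whole stratum as time 0 sets its loss to 1, an overstatement of 1 − p within the stratum. A proportion pooled over all children would be overstated by s × (1 − p).

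The documents give neither s nor p. For illustration, assume log-normal cumulative thresholds with median 1000 to 2500 mg and SD of the log 1.2 to 1.5. Then s, the probability of a threshold between 300 and 800 mg, is 13.3% to 26.8%. With 51 enrolled and 10% dropout (51 × 0.9 = 45.9, about 46), that is 46 × 0.133 = 6.1 to 46 × 0.268 = 12.3 children. A lower assumed share of 5% is 46 × 0.05 = 2.3. With p assumed between 0.25 and 0.75, the pooled overstatement runs from 0.05 × 0.25 = 1.25 points to 0.268 × 0.75 = 20.1 points. That width shows how little the documents determine.

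**The case against.** The strongest reply is that the SAP already contains the right answer. The passage in 10.1 is introduced as illustrative notation, and its rule in words concerns children who do not meet the MCRT, with the inequality only in parentheses. SAP 4.3 says what meeting the MCRT requires, and 10.1 fits its decay model, an exponential "distribution with log link for the decay of sensitivity threshold for those who take the final challenge". An analyst who reads 4.3 first would code the stratum correctly. This stands, and it limits the point to a wrong rule that is cheap to correct. It does not remove the point, because the inequality in 10.1 is what defines y_i.

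A second reply is that no sentence says the MCRT is cumulative. That is true. It follows from the wording about the amount consumed and from the absence of a 300 mg step. The step-scale disagreement between 10.1 and 8.1.2 does not depend on it.

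A reader might infer that the two rules clash over these children however the doses are expressed and wherever the 300 mg boundary falls. The documents do not support that. The clash holds under either boundary only on the step scale; on cumulative doses, with the inequalities as written, the rules agree on this child. Nor do the two boundary readings have equal weight, since the SAP's own entry rule admits exactly 300 mg.

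**Conclusion.** The point holds for d as SAP 10.1 defines it. Its time-zero rule misclassifies one of seven challenge outcomes, the step-3 reactors, against SAP 4.3 item 1 and the second synopsis bullet, and disagrees with SAP 8.1.2 on the same children. The effect falls on the time-zero mass (π and γ) and on the d = 200 stratum. Because the SAP analyses time to loss separately by 48-month dose interval, the curves for the other strata are not directly touched.

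The conclusion rests on the step arithmetic and on the SAP 4.3 entry rule being the one applied. If the sponsor instead requires more than 300 mg, 10.1 gives the intended zero on the step scale, and 8.1.2 then leaves step-3 reactors, who take no final challenge, without a time-zero code.

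A reader might also infer that the primary analysis fails or that the bias is large. Neither is shown. The number of children affected is not in the documents, every share in the illustration is assumed, and the finding does not depend on those figures. It should be fixed before the analysis dataset is built.

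**What to change.** 1. In SAP 10.1 and in 8.1.1/8.1.2, replace d < MCRT and LOAEL < MCRT with the SAP 4.3 item 2 rule: symptomatic at or below 300 mg cumulative, that is, a reaction at step 1 or step 2, so not eligible for the withdrawal phase.
2. Leave the SAP 8.1.3 rule, which counts withdrawals as failures at time 0, as a separate rule. The revised wording should not make ineligibility the only route to a time of zero.
3. State once whether NOAEL, LOAEL and d are single-step or cumulative doses, and use that scale throughout. Changing the scale without item 1 would only move the disagreement to step-2 reactors.
4. Align the first synopsis bullet and the Study Design text with SAP 4.3, so that a child who tolerates exactly 300 mg falls in one group. If the sponsor prefers to require more than 300 mg, SAP 4.3 and the second synopsis bullet must change instead, and the time-zero rule must also cover step-3 reactors.

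The cost is a few lines of SAP wording and one protocol clarification. No new data are needed.

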7. ANALYSIS POPULATIONS

The following analysis populations are planned for this study:

- **Safety Population (SAFETY):** all patients who receive at least 1 dose of investigational product. All safety analyses and demographic/baseline characterization will be performed using this population, analyzed as treated.
- **Intention-To-Treat Population (ITT):** all patients who are randomized for assessment of clinical desensitization and SU. This population is primary for efficacy and all efficacy analyses will be performed using this population.

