8.1.3 Data Handling for Patients who withdraw from the Study

Such subjects will be considered intolerant and failing at time 0.

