8.1.4 Imputation of Missing Data

No missing safety data will be imputed. For efficacy data with intermittent missingness, a subject will be considered failed at the first time when missingness is encountered.

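### The printed likelihood for time to loss of desensitization lets time-0 children into the event-time part, and SAP 8.1.2 and 8.1.3 code a child who withdraws after reaching MCRT in opposite ways

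*SAP*

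**What the plan says.** SAP 10.1 lets X_d be the time to loss for a child with 48th month NOAEL d, T the observation time with support 0 to 17 weeks, and Δ the indicator that X_d ≤ T. Children below MCRT at the 48th month challenge get X_d = 0, with probability π modelled by a logistic term in γ and flagged by y_i = 1. For the rest, F_d(t) = 1 − exp(−λt), with λ depending on covariates through β. The last printed line is, in effect,

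`π^y (1−π)^(1−y) × (1−F_d(t))^(1−δ) F_d(t)^δ g(t)`

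and the SAP concludes: "Maximizing the above likelihood will provide estimates of" β and γ.

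The rules that feed this model are:

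- Below MCRT: SAP 4.3 says such children "will be considered to have lost their desensitization at week 0". SAP 8.1.2 says those "who are not administered the final DBPCFC have their time to loss of desensitization assumed to be zero".
- No final challenge: SAP 8.1.2 says "For subjects who do not show up for the final DBPCFC until the 17th week of randomization will be removed from the analysis".
- Withdrawal from the study: SAP 8.1.3 says "Such subjects will be considered intolerant and failing at time 0".
- Intermittent missing efficacy data: SAP 8.1.4 says "a subject will be considered failed at the first time when missingness is encountered".
- Analysis set: SAP 7 bases all efficacy analyses on "all patients who are randomized for assessment of clinical desensitization and SU". SAP 4.3 makes reaching MCRT one of the criteria that "must be satisfied in order for the patient to continue to the SU phase of the study and be randomized".

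**The concern.** Time to loss, the proportion with loss at a fixed time and the hazard ratios are all primary endpoints (SAP 3.2.1), and this likelihood is the SAP's only explicit specification of how they are estimated. In a two-part model a time-0 child should inform π and nothing else. As printed, the child also enters F_d, so the model either cannot be maximized or overstates the loss rate.

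The withdrawal rules are a separate problem and a quieter one. Each runs without an error message, the curves by NOAEL interval in SAP 8.1 need the same coding decision, and the SAP does not rank the rules. The choice could therefore be made after withdrawals and outcomes are known. Coding time 0 also contradicts an observation: a child who reached MCRT at month 48 was desensitized at week 0.

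Finally, if only children who reach MCRT are randomized and only randomized children are analysed, the children who identify π are outside the analysis set.

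**Working it through.** **Plan's own figure.** The documents give none for this analysis. The only computed figure is the minimum of 50 subjects carried over from the two-arm design (Protocol 8.1.1). It reproduces: 50% against 90%, 2:1, two-sided 0.05 and 80% power give 30 + 15 = 45, and 45/0.9 = 50. This point does not affect it.

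**Step 1: a time-0 child with t = 0.** Assigned weeks run from 1 to 17 (SAP 4.3), so only a time-0 child can have t = 0. This is the natural value for a below-MCRT child, who gets no week. Then y = 1, δ = I(0 ≤ 0) = 1 and F_d(0) = 1 − e⁰ = 0. The printed contribution is π × 0 = 0 for every λ. With the F_d factors raised to (1 − y), it is π (0.10 if π = 0.10 is assumed), whatever λ and t are.

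**Step 2: a time-0 child with an assigned week.** A randomized child who withdraws and is coded time 0 under SAP 8.1.3 may keep the assigned week. The printed contribution is then π(1 − e^(−λt)). With π = 0.10 and λ = 0.1 (assumed) it is 0.0095 at week 1, 0.059 at week 9 and 0.082 at week 17. It is positive, but the child is counted twice, once in π and once as an event in F_d. To size this, take 45 children (Protocol 5.2) with weeks 1–17 equally likely, k of them time-0 children with δ = 1, and the rest with event probability 1 − e^(−λt). Solve the score equation Σ[δ t e^(−λt)/(1 − e^(−λt)) − (1 − δ)t] = 0 on expected data:

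| True median (weeks) | k = 3 | k = 5 | k = 9 |
|---|---|---|---|
| 4 | 3.8 | 3.6 | 3.3 |
| 8 | 7.3 | 6.8 | 6.0 |
| 17 | 14.2 | 12.7 | 10.3 |

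With the exponent added, the true median is returned in every case. The values of k and the medians are assumptions.

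**Step 3: the line above the expansion.** It multiplies a factor carrying I(X = 0) by one carrying I(X > 0). One of the two is always 0, so the product as printed is zero for every child. Its later terms do condition on X > 0, which shows that a two-part form was meant.

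**Step 4: where π can be estimated.** SAP 10.1 fits by NOAEL interval. Whether a child meets MCRT is determined by d, so within one interval y is constant apart from withdrawals coded time 0. π and γ therefore need a fit pooled over d.

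**Step 5: withdrawal after reaching MCRT, exponent corrected.** The quantity is the median of the overall loss curve among children who reached MCRT (n = 45, true value 8.0 weeks, withdrawal share w assumed). Under time-0 coding with unrelated withdrawal it is ln(2(1 − w))/λ with λ = ln 2/8, which gives 7.41 at 5% and 6.78 at 10%. The entries are medians over 3,000 simulated trials, except 9.3, which is the expected-data value (9.4 by simulation).

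| Withdrawal | Removed (8.1.2) | Time 0 (8.1.3) | Lost by assigned week |
|---|---|---|---|
| 5%, unrelated to loss | 8.0 | 7.4 | 7.4 |
| 10%, unrelated to loss | 7.9 | 6.8 | 6.8 |
| 5%, all already lost | 8.6 | 8.0 | 8.0 |
| 10%, all already lost | 9.3 | 7.9 | 8.0 |

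On the fixed-time endpoint, with 5 of 45 withdrawn and unrelated to loss, the proportion still desensitized at week 17 is 22.9% if they are removed and (40/45) × 22.9% = 20.4% at time 0. For a true median of 17 weeks the figures are 50.0% and 44.4%.

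For scale, with no withdrawal the central 95% of estimated medians runs from 5.2 to 12.7 weeks at n = 45, and from roughly 2.8 to 27.5 weeks in a stratum of 9.

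**The case against.** Much of the case for leaving the text alone concerns scope, and several parts of it stand.

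- A reader might infer that any fit containing a time-0 child is zero. The documents do not support this. SAP 8.1.3 sets the failure time to 0, not the observation time, and a randomized child has a week. The likelihood is zero only if t = 0; otherwise it is positive and biased.
- A reader might infer three conflicting rules. SAP 8.1.4 is limited to intermittent missingness, and permanent withdrawal before a single final challenge is not intermittent. It gives a third answer only on a loose reading.
- SAP 8.1.2 speaks of children who do not show up and SAP 8.1.3 of those who withdraw. SAP 1 and 4.5 describe no-shows who stay in the study and may be challenged later. Read by heading, the two rules could address different groups. This narrows the conflict but does not remove it, because a child who withdraws after month 48 also never attends the final challenge and so meets both rules.
- On the analysis set, SAP 4 can be read as randomizing at the 48th month visit generally, which would keep below-MCRT children in ITT. SAP 4.3 points the other way, so the text needs to say which holds.
- A reader might take the 10% drop-out in Protocol 5.2 as the withdrawal rate here. It applies before randomization; no document gives a rate after the 48th month challenge.
- A reader might infer that the choice between 8.1.2 and 8.1.3 distorts the hazard ratios. With the exponent added it does not: time-0 coding then enters π only.

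It is also fair to say that the repair to the formula is evident, and that the simulations planned in SAP 6 could expose the fault before trial data are used. A conversion fault in the formula is unlikely, because both lines that carry exponents agree.

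**Conclusion.** The likelihood is wrong as written, and SAP 8.1.2 and 8.1.3 contradict each other for a child who reached MCRT and withdrew before the final DBPCFC. The first conclusion needs no assumption: the (1 − y_i) exponent is absent, and the result is a zero likelihood at t = 0 or double counting at an assigned week. The size of the double counting (8 weeks estimated as 6.8, 17 as 12.7) rests on an assumed 5 of 45 time-0 children, weeks uniform on 1–17 and one pooled exponential.

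The choice of withdrawal rule moves the overall median by about 0.6 weeks at 5% and 1.1 to 1.4 weeks at 10% assumed withdrawal. That is smaller than sampling error, but it is systematic and open to choice after the fact. It affects π and the overall loss curve, not F_d or the hazard ratios given X > 0 once the exponent is in place. The gap in the analysis set is an ambiguity that depends on which of SAP 4 and 4.3 governs.

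**What to change.** In SAP 10.1, write

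`P_i = π_i^(y_i) × [(1−π_i) (1−F_d(t_i))^(1−δ_i) F_d(t_i)^(δ_i)]^(1−y_i)`

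and correct the line above it to match. State that π and γ are estimated, pooled over d, on all children who took the 48th month DBPCFC, randomized or not, and that F_d is estimated on those who took the final DBPCFC. Align SAP 7 with this.

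Replace SAP 8.1.3 and the no-show bullet in 8.1.2 with one rule for this endpoint: a child who reached MCRT but has no final DBPCFC is not coded X = 0 and contributes only 1 − π_i. Say that 8.1.4 does not apply to this case. Keep the drop-out analysis already planned in 8.1.2. Report two labelled sensitivity analyses: failure at time 0, as 8.1.3 now has it, and lost by the assigned week (δ = 1 at that week). State also whether withdrawals before the 48th month challenge, who have no measured threshold, are outside this model.

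The cost is SAP wording and a few lines of code. The downside is that the main rule assumes withdrawal is unrelated to loss and can be anti-conservative: about 8.6 weeks at 5% and 9.3 at 10% assumed withdrawal, against a true 8.0, if every withdrawn child had already lost desensitization. The two sensitivity codings give 7.9 to 8.0 in that case, so reporting all three shows the range.
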